## 12.3 Handling of Missing, Unused, and Spurious Data

### 12.3.1 Missing Date Information for Prior or Concomitant Medications (Therapies/Procedures)

For prior or concomitant medications (and/or therapies/procedures), incomplete (ie, partially missing) start date and/or stop date will be imputed. When the start date and the stop date are both incomplete for a subject, impute the start date first.

#### 12.3.1.1 Incomplete Start Date

The following rules will be applied to impute the missing numerical fields. If the stop date is complete and the imputed start date is after the stop date, then the start date will be imputed using the stop date.

#### 12.3.1.2 Missing Day and Month

- If the year of the incomplete start date is;
  - The same as the year of the date of the first dose of IP, then the day and month of the date of the first dose of IP will be assigned to the missing fields.
  - Before the year of the date of the first dose of IP, then December 31 will be assigned to the missing fields.
  - After the year of the date of the first dose of IP, then 01 January will be assigned to the missing fields.

##### 12.3.1.2.1 Missing Month Only

- The day will be treated as missing and both month and day will be replaced according to the above procedure.

##### 12.3.1.2.2 Missing Day Only

- If only day is missing and the month and year of the incomplete start date are the same as the month and year of the date of the first dose of IP, then the day of the date of the first dose of IP will be assigned to the missing day.
- If either the year is before the year of the date of the first dose of IP or if both years are the same but the month is before the month of the date of the first dose of IP, then the last day of the month will be assigned to the missing day.
- If either the year is after the year of the date of the first dose of IP or if both years are the same but the month is after the month of the date of the first dose of IP, then the first day of the month will be assigned to the missing day.

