8.8 Safety Analyses

The Safety Set will be used to summarize safety data. Safety will be assessed for the following evaluations:

- Number, severity, seriousness, and causality of TEAEs
- Changes in vital signs ECGs, and clinical laboratory results (hematology, chemistry, and urinalysis) from baseline to post-baseline time points. Baseline is defined as the last non-missing assessment prior to the first dose.

Safety data, including TEAEs, 12-lead ECGs, vital signs (systolic and diastolic blood pressure, pulse rate, respiratory rate), and clinical laboratory data (biochemistry, hematology, and urinalysis), will be summarized with the descriptive statistics. Potentially clinically important findings will also be summarized or listed. The potentially clinically important values will be defined in the SAP.

Quantitative safety data as well as the difference from baseline, if applicable, will be summarized by descriptive statistics. Frequency counts will be compiled for classification of qualitative safety data. Direct safety comparisons between the two cohorts (the subjects of Japanese descent and Non-Hispanic Caucasian subjects) will be presented from the maribavir 400 mg dosing data. All other safety data from the 200 mg and 800 mg in the subjects of Japanese descent will be summarized and listed.

For each safety variable, the last value collected before the first dose of investigational product in that treatment period will be used as baseline for all analyses of that safety variable in that treatment period.

An AE (classified by preferred term [PT]) that occurred during the study will be considered a TEAE if it had a start date on or after the first dose of investigational product or if it had a start date before the date of the first dose of investigational product, but increased in intensity on or after the date of the first dose of investigational product. An AE that occurred after the follow-up phone call will not be counted as a TEAE.

Adverse events will be coded using the agreed-upon version of Medical Dictionary for Regulatory Activities, Version 23.0. or later. The number of events, incidence, and percentage of TEAEs will be calculated overall, by system organ class, and by PT. Treatment emergent adverse events will be further summarized by severity and relationship to investigational product. Adverse events related to investigational product, AEs leading to withdrawal, SAEs, and deaths will be similarly summarized/listed.

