### 7.1 Adverse Events

Adverse events will be coded using MedDRA Version 23.0 or newer.

An AE (classified by preferred term) that occurs during the study will be considered a TEAE if it has a start date on or after the first dose of investigational product or if it has a start date before the date of the first dose of investigational product, but increases in severity on or after the date of the first dose of investigational product. If more than 1 AE with the same preferred term is reported before the date of the first dose of investigational product, then the AE with the greatest severity will be used as the benchmark for comparison to the AEs occurring during the study under the preferred term. Adverse events during the study will be assigned to the treatment(s) a subject has taken at the onset of the event. An AE with start date and time during the wash-out period or the 7 days follow-up period after last single dose of IP will be assigned to the prior treatment subject received. An AE that occurs more than 7 days after the date of the last dose of investigational product will not be counted as a TEAE.

An overall summary of the number of subjects with TEAEs as well as the number of events will be presented, including the number and percentage of subjects with any TEAEs, serious TEAEs, TEAEs related to investigational product and TEAEs leading to discontinuation of investigational product.

The number and percentage of subjects reporting TEAEs, as well as the number of events, in each cohort, each treatment group, and overall will be tabulated by system organ class (SOC) and preferred term (PT); by SOC, preferred term (PT), and maximum severity. TEAEs considered related to investigational product will also be summarized by SOC and preferred term. If more than 1 AE occurs with the same preferred term for the same subject, then the subject will be counted only once for that preferred term using the most severe and most related occurrence for the summarization by severity and by relationship to investigational product. Presentation by SOC and PT will present SOC sorted alphabetically and PT within SOC by descending incidence.

TEAEs and related TEAEs will be summarized by preferred term by descending frequency. Serious TEAEs, TEAEs leading to discontinuation of investigational product and serious TEAEs leading to death, will be summarized by SOC, preferred term, cohort, and treatment group.

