### 12.3.2.1 Incomplete Start Date

Follow the same rules as in Section [12.3.1.1](#).

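### Partial adverse-event start dates default to the first dose, which can move a Japanese 200 or 800 mg event into the 400 mg column used to compare the cohorts (minor)

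*SAP*

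**What the plan says.** SAP 12.3.2.1 has no start-date rule of its own for AEs. It reuses the medication rules: "Follow the same rules as in Section" 12.3.1.1. Those rules have these branches:

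- Day missing, same month and year as the first dose: "then the day of the date of the first dose of IP will be assigned to the missing day".
- Day missing, earlier month: "then the last day of the month will be assigned to the missing day".
- Day missing, later month: "then the first day of the month will be assigned to the missing day".
- Day and month missing, same year as the first dose: "then the day and month of the date of the first dose of IP will be assigned to the missing fields".
- If the imputed start falls after a complete stop date, "then the start date will be imputed using the stop date".

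On dose attribution, SAP 7.1 says: "Adverse events during the study will be assigned to the treatment(s) a subject has taken at the onset of the event". Events starting in a washout or in the 7-day follow-up go to the preceding treatment.

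Under SAP 3.1 both cohorts receive 400 mg in Period 1. The Caucasian cohort has that period only. The Japanese cohort goes on to 200 and 800 mg in randomized order. Protocol 8.8 says that the direct safety comparisons between cohorts "will be presented from the maribavir 400 mg dosing data".

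**The concern.** Dating an uncertain onset to the first dose is a cautious convention when a subject has one dose, because the event is then kept as treatment-emergent. With three doses, the same date also selects a dose, and it selects the earliest one. In the Japanese cohort that is always 400 mg.

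A Japanese event that followed 200 or 800 mg would therefore leave its own column and enter the 400 mg column. A Caucasian event cannot move between doses. Safety at each of the three doses in Japanese subjects is a secondary objective, and Protocol 2.1 says the results will guide dose selection for a later Japanese study. With 12 subjects per cohort, one misplaced subject is visible in a table.

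**Working it through.** The plan gives no figure on this point, so there is none to reproduce. The check applies the SAP rules to every calendar position.

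**Inputs from the documents**
- Japanese doses are 72 to 73 hours apart (Protocol Table 1, footnote i), so they fall on days 0, 3 and 6 from the first dose.
- A treatment-emergent AE starts no later than 7 days after the last dose (SAP 7.1), so up to day 13 for Japanese subjects and day 7 for Caucasian subjects.
- There are 12 subjects per cohort (SAP 3.4). The study is planned for about August to November 2020 (Protocol synopsis).

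**Assumptions**
- First-dose dates run from 1 August to 15 November 2020: 31 + 30 + 31 + 15 = 107 dates.
- All onset days weigh equally.
- Imputed dates are used for dose attribution.
- The stop-date check is not modelled.

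**Day missing, true onset after 200 or 800 mg (days 3 to 13)**
- Onset-days: 11 × 107 = 1177.
- Three month-ends can be crossed, so an onset on day k stays in the first-dose month for 107 − 3k first-dose dates. Summed over k = 3 to 13: 1177 − 3 × 88 = 913. All are dated to the 400 mg dose.
- A later-month date goes to the 1st. If the 1st falls 1 or 2 days after the first dose, that is still Period 1. This covers 2 × 3 = 6 first-dose dates and 6 × 11 = 66 onset-days.
- Moved to 400 mg: 913 + 66 = 979 of 1177 (83%).
- The other 198 (17%) keep a Period 2 or 3 dose: 126 the right one, and 72 moved from Period 3 to Period 2. Example: with doses on 22, 25 and 28 September, a true onset of 2 October becomes 1 October, which is still Period 3.

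**After discharge only.** In-house days are the least likely to have partial dates, so take days 7 to 13. There are 7 × 107 = 749 onset-days. Moved to 400 mg: the sum of (107 − 3k + 6) over k = 7 to 13, which is 791 − 210 = 581 (78%).

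**Day and month missing.** All 1177 of 1177 move to 400 mg.

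**Opposite direction.** True Japanese 400 mg onset-days that leave 400 mg: 0 of 321 (3 × 107). The one theoretical exception is an onset before dosing on the Period 2 dosing date when that date is the 1st of a month.

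**Caucasian cohort.** Moves between doses: 0 of 856 (8 × 107). With the day missing, the rules do turn 1463 of 2996 pre-dose onset-days (28 × 107) and 398 of 428 late ones (days 8 to 11) into 400 mg treatment-emergent events. The Japanese pre-dose count is the same, 1463 of 2996. For late Japanese onsets, 263 of 428 go to 400 mg.

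**Stop-date check.** It acts only when the imputed start is later than a complete stop date. A Period 2 or 3 event ends after the first dose, so the check cannot correct the between-dose shift. It would reduce the pre-dose counts above for events that had already resolved.

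**Size.** One subject is 1/12 = 8.3 points and two are 2/12 = 16.7 points. These are ceilings. SAP 7.1 counts a subject once per preferred term, so incidence does not change if the subject already had that term at 400 mg, although the event count still rises by one.

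The 83% and 78% are shares of calendar positions. They are not rates of misplaced AEs.

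**The case against.** The strongest objection is that SAP 12.3.2 presents AE date imputation as an optional aid for deciding whether an event is treatment-emergent. It does not say that the imputed date sets the dose. SAP 7.1 places washout and follow-up events by date and time, and the imputation supplies no time. This stands as far as it goes: using the imputed date for dose attribution is an inference. But SAP 7.1 needs an onset date, and the SAP provides no other date and no separate rule for a partial date in a three-dose subject. A programmer following the text would use the imputed date.

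The second objection is rarity, and it largely stands. Japanese subjects check in on Day -1 and leave on Day 2 of Period 3. They are asked about AEs at each visit and after each washout, and unclear data are queried. Protocol 1.2.5 says that dysgeusia, the most common event, usually starts within an hour of dosing, so while subjects are in-house. The main exposed interval runs from discharge to the follow-up call. An event that newly arises there follows the last dose, which is where a Period 1 date is wrong.

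Third, the comparison is descriptive, with no test or decision rule. That also stands and limits the consequence.

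A reader might infer that every partial date goes to the first dose. The documents do not support this: earlier-month dates become pre-dose, and later-month dates go to the 1st and may keep a later dose. A reader might also infer that Caucasian partial-date events are always placed correctly, so that only the Japanese column can be inflated. That is not so: pre-dose and late events can be pulled into 400 mg in both cohorts. Only the shift between doses is specific to the Japanese cohort.

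**Conclusion.** The point holds in a limited form and is minor. Read with SAP 7.1, the imputation rule would move a Japanese event after 200 or 800 mg to 400 mg when its start day is missing in the first-dose month, or its day and month are missing in the first-dose year. It does the same for a later-month date if the 1st falls before the second dose. For the 400 mg column this between-dose shift runs one way, apart from the boundary case noted above, and it cannot occur in the Caucasian cohort.

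The effect is at most 8.3 points per affected subject. It is zero if all start dates are complete, and zero for the incidence of a term the subject already had at 400 mg. The number of partial dates is unknown and probably small. The conclusion assumes that imputed dates would be used for dose attribution. It might be read as showing a bias built into the safety comparison. The documents do not go that far, because they never state that link and give no frequency of partial dates.

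**What to change.** State in SAP 12.3.2 that imputed start dates decide treatment-emergent status only. For Japanese subjects, attribute a partial-date AE to a dose from three sources:

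- the known parts of the start date;
- the stop date;
- the interval between the AE query at which the event was first reported and the query before it.

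An event that newly arose and was first reported at the follow-up call then goes to the last dose received. Flag and list any event that stays ambiguous, and show the 400 mg comparison with and without it. Counting an ambiguous event under every possible dose is a weaker choice, because it keeps part of the 400 mg inflation and counts the event more than once.

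The cost is a few lines of SAP text, some extra programming and a few flagged events. The AE queries are already scheduled. The documents do not say whether the case report form records the query at which an event was first reported, so that should be confirmed before database lock.

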#### 12.3.1.3 Incomplete Stop Date

The following rules will be applied to impute the missing numerical fields. If the date of the last dose of IP is missing, then replace it with the last visit date. If the imputed stop date is before the start date (imputed or non-imputed start date), then the imputed stop date will be equal to the start date.

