#### **5.4 Prior Medications (Therapies), and Procedures**

All prior medications, therapies, and procedures will be listed based on the Safety Set. Prior medications will be coded using the World Health Organization Drug Dictionary Global B3 dated March 2020.

Prior medications (therapies) and procedures are defined as the medications (therapies) and procedures with a start date prior to the date of the first single dose of IP.

Prior medication usage presented by therapeutic class according to Anatomical Therapeutic Chemical (ATC) classification and PT will be summarized based on the number and proportion of subjects in each cohort and in overall subjects based on the Safety Set. Multiple medication usage by a subject in the same category will be counted only once.

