## 12.3.2 Missing Date Information for Adverse Events

For AEs with partial start dates, non-missing date parts will be used to determine if the AE is a TEAE or not. If a determination cannot be made using the non-missing date parts as to when the AE occurred relative to study drug administration, eg AE start year and month are the same as the year and month of the first dose of IP, then the AE will be classified as a TEAE.

To facilitate categorization of AEs as TEAEs, imputation of dates can be used. For AEs, the default is to only impute incomplete (ie, partially missing) start dates. Incomplete stop dates may also be imputed when calculation of the duration of an AE is required per the protocol. If imputation of an incomplete stop date is required, and both the start date and the stop date are incomplete for a subject, impute the start date first.

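### When both medication dates are partial, SAP 12.3.1 can replace a stop month that proves a pre-dose end with a guessed date on the 400 mg dosing day

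*SAP*

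**What the plan says.** SAP 12.3.1 fixes the order of work for medications: "When the start date and the stop date are both incomplete for a subject, impute the start date first". Under 12.3.1.2, if a start date lacks day and month and its year is the dosing year, "then the day and month of the date of the first dose of IP will be assigned to the missing fields". Under 12.3.1.3.3, a stop date lacking only the day, in a month before the month of the last dose, goes to the last day of its month. SAP 12.3.1.3 then adds that if the imputed stop is "before the start date (imputed or non-imputed start date), then the imputed stop date will be equal to the start date".

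SAP 12.3.1.1 contains a safeguard in the other direction, limited to complete stop dates: if "the imputed start date is after the stop date, then the start date will be imputed using the stop date".

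SAP 5.4 defines prior medications as those "with a start date prior to the date of the first single dose of IP". SAP 5.5 treats a medication as concomitant to whatever study treatment was taken while it was in use. The first dose is 400 mg for every subject (SAP 3.1).

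For AEs, SAP 12.3.2 uses the non-missing date parts to decide treatment-emergent status and defaults to treatment-emergent if they do not settle the matter. Its example is that "AE start year and month are the same as the year and month of the first dose of IP". By default only AE start dates are imputed. SAP 12.3.2.1 sends them to the rules of 12.3.1.1.

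**The concern.** A recorded stop month is data; a start date filled in from the year alone is a guess. The safeguard in 12.3.1.1 shows that the plan means stop-date evidence to prevail over a guessed start. For a partial stop date the order of steps does the opposite: the guess is made without looking at the stop, and the stop is then moved to fit the guess.

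At stake are the medication tables. The record no longer counts as prior, because its start is no longer before the first dose. It counts instead as taken with the 400 mg dose, the dose at which the two cohorts are compared. Neither statement agrees with what was recorded.

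**Working it through.** The plan gives no figure on this point, so there is none to reproduce. The check applies the written rules to one record and then to every combination of date completeness.

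**Inputs.** F is the first-dose date, L the last-dose date, S the imputed start, E the imputed stop.
- Start with the dosing year only: S = F (12.3.1.2).
- Stop with the day missing, in a month before L's month: E = last day of that month (12.3.1.3.3).
- If E < S, then E = S (12.3.1.3).
- Complete stop date with S after it: S = stop date (12.3.1.1).
- Prior if S < F (5.4).
- Assumed F = 14 Sep 2020, inside the planned study period of about Aug to Nov 2020 (Protocol synopsis). L = 14 Sep for a Caucasian subject. With two 72-hour intervals, L = 14 + 2 × 3 = 20 Sep for a Japanese subject. Both give the same results below.

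**Single records.**

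| Recorded start | Recorded stop | S | E | Reported as |
|---|---|---|---|---|
| 2020 | Aug 2020 | 14 Sep | 31 Aug, then reset to 14 Sep | concomitant with 400 mg, not prior |
| 2020 | 20 Aug 2020 | 14 Sep, then reset to 20 Aug | 20 Aug | prior only |
| Aug 2020 | Aug 2020 | 31 Aug | 31 Aug | prior only |

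The first two rows both describe a medication that ended in August. Less detail in the stop date changes the classification, even though the month alone settles the question.

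**All patterns.** Each date may be complete, lack the day, or lack day and month: 3 × 3 = 9 patterns. Take F = 20 Aug 2020 (assumed), starts 1 to 230 days earlier, and stops on or after the start but before F. That gives 230 × 231 / 2 = 26,565 date pairs. Where the stop lacks the day, only a stop in July or earlier (20 or more days before F) proves a pre-dose end: 211 × 212 / 2 = 22,366 pairs. Pairs that provably ended before dosing but receive a stop on or after the first dose:

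| Start recorded as | Stop complete | Stop lacks day | Stop has year only |
|---|---|---|---|
| Complete | 0 of 26,565 | 0 of 22,366 | none provable |
| Lacks day | 0 of 26,565 | 0 of 22,366 | none provable |
| Year only | 0 of 26,565 | 22,366 of 22,366 | none provable |

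The counts are the same with L = 20 Aug or 26 Aug. If the safeguard is extended to partial stop dates, the failing cell becomes 0 of 22,366 and the others do not change. These are counts of possible date pairs, not of expected subjects.

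**AEs.** The reset in 12.3.1.3 does not normally run, because AE stop dates are not imputed by default. Two cases show what the text leaves open, with F = 14 Sep 2020:
- Start Sep 2020, complete stop 8 Sep 2020. Through 12.3.2.1 and 12.3.1.1 the start becomes 8 Sep, so the event is pre-treatment. The month-match example in 12.3.2, read alone, makes it treatment-emergent.
- Start 2020, stop Aug 2020. The start is imputed to 14 Sep, so the event is treatment-emergent unless the non-missing date parts are taken to include those of the stop date. 12.3.2 does not say.

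**Size per record.** One subject in a cohort of 12 is 1/12 = 8.3 percentage points.

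**The case against.** The strongest reply is that the gap is narrow. It needs a start with year only together with a stop that has month and year. Protocol 5.1 sends to the CRF treatments received within 30 days before the first dose (or five half-lives, if longer). For a first dose on 14 Sep, 30 days reaches back to 15 Aug, so a stop of Jul 2020, at least 45 days before dosing, would usually not be in the database. Exclusion 18 further limits what a subject may have taken. Protocol 8.2 provides for queries on omissions. What remains is mainly over-the-counter or excepted products stopped in the previous calendar month. All of this stands. It limits the frequency but does not make the rule right for the records it reaches.

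A reader might infer more than the documents support:
- *Any recorded stop date can be overridden.* It cannot: 12.3.1.1 protects every complete stop date.
- *The AE rules contradict each other.* The month match in 12.3.2 is an example of timing that cannot be determined. Read with 12.3.2.1, a complete pre-dose stop makes the timing determinable. The wording is unclear rather than contradictory, and defaulting to treatment-emergent when timing is unknown is deliberately conservative, like the missing-severity and missing-relationship rules in 12.3.3 and 12.3.4.
- *About half of screening AEs with a missing start day are misclassified.* With first doses uniform over Aug to Nov 2020, onset 1 to 28 days before dosing and durations of 1 to 3 days ending before dosing, 5026 of 9882 combinations (50.9%) have onset in the dosing month. That is a share of onsets, not an error rate.
- *Misdated records would appear as breaches of exclusion 18, or as events caused by the drug.* Deviations are recorded by the site in a separate tracker (SAP 5.8). Relatedness is the investigator's judgement (Protocol Appendix 2.3) and is imputed only if missing.

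**Conclusion.** The point holds for medications with a year-only start in the dosing year and a stop whose recorded month lies before the first-dose month. For these the written rules always give a wrong date and a wrong classification; this is a stated rule producing an error, not a missing detail. One of nine patterns is affected. The 100% failure rate applies within that pattern only and says nothing about how often it occurs. The documents do not give that frequency, and it is probably low. The dosing dates used in the check are assumptions.

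For AEs the conclusion is weaker: the text should say that stop-date information counts, and a few treatment-emergent counts could depend on it. The primary PK endpoints are unaffected. This is a small correction, worth making because it is cheap and the error can be shown from the rules themselves.

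**What to change.** In SAP 12.3.1.1, extend the safeguard to partial stop dates. Suggested text: *If the stop date, or its non-missing parts, falls before the imputed start date, the start date will be set to the latest date consistent with the stop date, that is, the stop date if complete, otherwise the last day of the recorded stop month or year.* The example then becomes 31 Aug to 31 Aug 2020, prior only.

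Keep the reset in 12.3.1.3 for starts that are not imputed. A rule forbidding any move of an imputed stop outside its recorded month would be a poor substitute: where a complete start is later than the recorded stop month, it would leave the stop before the start.

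In SAP 12.3.2, add: *The non-missing date parts include those of the stop date; an AE whose stop date or its non-missing parts show that it ended before the first dose of IP is not a TEAE.* Keep the default to treatment-emergent for events whose timing is truly undetermined.

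The cost is two sentences and a small change to the date-imputation program. No new data or procedures are needed. Reported concomitant medications and TEAEs may fall slightly.
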